3 STUDY PLAN

3.1 Overall Study Design and Plan

The study visit schedule and planned assessments at each visit are detailed in Table 1.

This is a Phase 2a, open-label, single-arm study to investigate the safety, tolerability, efficacy, PK, and PD of ATI-450 to maintain remission in patients with CAPS previously managed with anti-IL-1 therapy. Up to 10 patients are planned to be enrolled in the study. The study will consist of an up to 8-week screening period, a 12-week treatment period, and a 4-week safety follow-up period. The total duration of the study for patients remaining in the study until their final safety follow-up assessment will be up to 24 weeks.

The investigator will obtain signed informed consent from the patient before any study procedures are performed. For further details regarding the informed consent process, see Section 9.3. During the screening visit each patient will be required to have all assessments performed as outlined in the Schedule of Assessments (Table 1).

Patients whose eligibility is confirmed at baseline will begin dosing ATI-450 tablets (50 mg BID). Such patients will be in protocol-defined remission due to prior treatment with an anti-IL-1 biologic. Dosing will begin on the day that the next dose of their anti-IL-1 therapy is scheduled at which time anti-IL-1 therapy will be discontinued.

The first dose of ATI-450 (50 mg BID) will be taken at the following times (based on anti-IL-1 therapy):

- Anakinra: 24 hours (+/- 1 hour) after last administration or at approximate time of regular anakinra dose.
- Canakinumab: 8 weeks (+/- 1 week) after last administration.
- Rilonacept: 1 week (+/- 1 day) after last administration.

ATI-450 will be administered orally for 12-weeks. Patients will attend clinic visits on Days 14, 28, 56, and 84 (+/-1 day) for safety, efficacy, PK and PD assessments. Patients will begin recording disease symptoms in their daily diary card 7 days prior to beginning administration of ATI-450, or immediately starting at the screening visit if the Day 1 visit is scheduled to occur less than 7 days after the screening visit. Patients will continue to complete their diary until completion of the safety follow up Day 7 visit.

At the end of 12-weeks, Day 84 (+/- 1 day), patients will stop ATI-450 and conduct end of study assessments. Patients will complete safety follow-up visits on site 7 Days (+4 days) after the last dose of ATI-450 and via a phone call 30 Days (+/-3 days) after the last dose.

Patients should not start their anti-IL-1 therapy until all safety follow-up Day 7 assessments have been completed. However, in the event of a safety concern, patients will be allowed to return

early or restart their anti-IL-1 therapy prior to completing the safety follow-up Day 7 visit at the discretion of the investigator.

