	Visit 1 Day -56 to Day -1	Visit 2 Baseline Day 1	Visit 3 Day 14	Visit 4 Day 28	Visit 5 Day 56	Visit 6 Day 84 EOS	Visit 7 Day 7 ⁶	Visit 8 Phone Call Day 30
				(+/-1 day)			(+4 days)	(+/-3 days)
PD Blood Sampling ²		X	X	X	X	X	X	
PK Blood Sampling ²		X	X	X	X	X	X	
Serum Pregnancy	X							
Urine Pregnancy		X	X	X	X	X	X	
Dispense Study Medication		X	X	X	X			
Administration of Morning Dose of ATI-450 in Clinic ⁷		X	X	X	X	X		
Drug Accountability			X	X	X	X		
Adverse Events ⁵	X	X	X	X	X	X	X	X
Prior and Concomitant Medications	X	X	X	X	X	X	X	X

ECG=electrocardiogram, Hep=hepatitis, PD=pharmacodynamic, TB=tuberculosis, EOS=end of study

¹A full physical examination will be performed at screening. The brief physical examination (including signs of CAPS) will be performed at visit 6 and follow-up. Body mass index will be derived in the eCRF.

²On dosing day(s), patient diary, PGA, KSS, vitals, clinical laboratory parameters, PK, and PD will be performed before the administration of study medication.

³Vital signs will be measured prior to dosing and immediately following dosing in a semi supine position after 5 minutes' rest and will include temperature, systolic and diastolic blood pressure, pulse, and respiratory rate.

⁴ A triplicate 12-lead ECG will be recorded after the subject has been resting for at least 5 minutes in a supine position.

⁵Serious adverse event reporting will start at the time of consent. Any AE that occurs between the time of consent and dosing on Day 1 will be recorded as medical history. Treatment-emergent AEs will be collected following the first dose of study medication on Day 1.

⁶Patients should not start their anti-IL-1 therapy until all safety follow-up Day 7 assessments have been completed. However, in the event of a safety concern, patients will be allowed to return early or restart their anti-IL-1 therapy early prior to completing the safety follow-up Day 7 visit at the discretion of the investigator.

⁷ The last dose of ATI-450 will be administered in clinic on Day 84. The second dose of ATI-450 is not to be administered on Day 84.

⁸ Patients will be instructed on how to complete their patient diary at the screening visit. Patients will begin completing the patient diary 7 days prior to beginning ATI-450 administration (Day 1), or immediately beginning at the screening visit if the Day 1 visit is scheduled to occur less than 7 days after screening.

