3.3 End of Study

A patient is considered to have completed the study if he/she has completed all study visits. The end of the study is defined as the date of the last visit or date of last procedure of the last patient in the study.

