7.3 Documenting and Reporting Adverse Events

Reporting of SAEs will begin when the patient has provided informed consent and will continue up to the end of study visit or 30 days after the last ATI-450administration whichever is later. Reporting of AEs will begin when the patient receives the first dose of ATI-450 and will continue up to the end of study visit or 30 days after the last study drug administration, whichever is later. Any clinical AE that occurs between the time of consent and dosing Day 1 will be recorded as medical history.

Occurrence of AEs may be volunteered spontaneously by the patient; discovered as a result of general, nonleading verbal questioning by the study staff; or determined by physical examination or other safety assessments. All AEs will be monitored and recorded in the CRF throughout the entire study.

For all AEs, the investigator must pursue and obtain adequate information (a description of the event, severity, time of occurrence [including whether the AE onset was before, during, or after the study medication administration if the AE started on a dosing day], duration, and any action [e.g., treatment/follow-up tests]). The outcome of the event should be provided along with the investigator's assessment of the relationship to the study medication. The investigator must also assess whether the event meets the criteria for classification as an SAE.

It is the investigator's responsibility to review all documentation (e.g., hospital notes, laboratory reports, and diagnostic reports) related to an AE. Wherever possible, the investigator's diagnosis, not the individual signs and symptoms, will be documented as the AE.

Investigators are not obligated to actively seek AEs or SAEs after the patient's conclusion of study participation. However, if the investigator learns of any SAE, including death, at any time after a patient has been discharged from the study, and he/she considers the event to be reasonably related to the study medication or study participation, the investigator must promptly notify the sponsor.

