8.2 Analysis Populations

- The ITT population will include all patients who have been administered at least one dose of study medication.
- The PP population will include all patients who complete 12-weeks of treatment and 4-weeks of follow up and have completed assessments.

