8.4.2 Safety Analyses

The Safety population will be used for the analysis of safety data (AEs, exposure to study medication, clinical laboratory, vital signs, and ECG).

AEs will be coded with the MedDRA. TEAEs are defined as AEs with an onset date on or after the date of first administration of study medication and before the date of last administration of study medication + 30 days. TEAEs will be presented by system organ class and preferred term in frequency tables. Patients with multiple AEs will be counted only once within each preferred term and system organ class. Key patient information for patients with an AE with an outcome of death, patients with SAEs, and patients with an AE leading to discontinuation of study medication will be listed.

Laboratory data (hematology, serum chemistry, coagulation, lipids, and urinalysis) will be converted to Système International units for reporting and processing purposes. Absolute values and changes from baseline will be presented descriptively. Laboratory data outside study-specific reference ranges will be listed.

Vital signs and ECG parameters will be presented descriptively.

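### An on-schedule final safety call on post-dose Days 27 to 29 ends active adverse event inquiry before the 30-day reporting period closes, and the TEAE cut-off leaves out a Day 30 onset that Section 7.3 collects

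*Combined protocol and SAP*

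**What the plan says.** - **Final contact.** Section 3.1 schedules an on-site visit 7 days (+4) after the last dose and then a last contact "via a phone call 30 Days (+/-3 days) after the last dose". The synopsis and the Visit 8 column of Table 1 give the same timing. Nothing is scheduled later.
- **Reporting period.** Section 7.3 says that AE reporting starts at the first dose and "will continue up to the end of study visit or 30 days after the last study drug administration, whichever is later". SAE reporting starts at consent and has the same end.
- **After participation.** Section 3.3 states: "A patient is considered to have completed the study if he/she has completed all study visits". Section 7.3 adds that investigators need not actively look for events once participation is over.
- **Analysis window.** Section 8.4.2, like the synopsis, defines a TEAE as an AE with onset on or after the first dose and "before the date of last administration of study medication + 30 days". The AE frequency tables by system organ class and preferred term are built on TEAEs.
- **Role of the data.** Section 2 (Table 2) makes the number and percent of AEs and SAEs part of the primary endpoint.

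**The concern.** Three clocks govern the same data: the call window, the reporting period and the TEAE window. They do not end together. If the call may fall before the reporting period closes and nothing follows it, the last days of that period are not asked about. Which patients this affects depends only on when the site happened to ring.

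The strict cut-off in 8.4.2 adds a one-day mismatch for every patient, whenever the call is made. An event starting on Day 30 is reportable under 7.3 but falls outside the TEAE tables.

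At stake is even and complete ascertainment of AEs, the primary data in a single-arm study of at most 10 patients.

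**Working it through.** **Inputs**
- Call: 30 days after the last dose, +/-3 (3.1, synopsis, Table 1).
- End of AE/SAE reporting: the later of the end of study visit and last dose + 30 days (7.3).
- TEAE onset: strictly before last dose + 30 days (8.4.2, synopsis).
- Treatment length: nominally 84 days (3.1).

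**Step 1: when reporting ends.** Table 1 labels Visit 6 (Day 84) as EOS. The later of the two dates is therefore last dose + 30 days. If a reader took the Day 30 call to be the end of study visit instead, the later-of rule would still not end reporting before Day 30.

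**Step 2: permitted call days.** 30 - 3 = 27 and 30 + 3 = 33, so seven days are allowed (27 to 33). Three of them (27, 28, 29) precede Day 30.

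**Step 3: days not asked about.** Let the call be on post-dose day c, and assume that it covers events up to and including that day. Uncovered reporting days are max(0, 30 - c). Because TEAE onset must precede Day 30, uncovered TEAE days are max(0, 29 - c).

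| Call day c | Reporting days not covered | Of these, TEAE days |
|---|---|---|
| 27 | 3 (Days 28, 29, 30) | 2 (Days 28, 29) |
| 28 | 2 (Days 29, 30) | 1 (Day 29) |
| 29 | 1 (Day 30) | 0 |
| 30 to 33 | 0 | 0 |

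**Step 4: size.** AE collection for a completer lasts about 84 + 30 = 114 days. At worst, 3 / 114 = 2.6% is not actively queried. The TEAE window is 84 + 29 = 113 days, and at worst 2 / 113 = 1.8% of it is not queried.

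**Step 5: the Day 30 mismatch.** An onset exactly 30 days after the last dose lies within 7.3 but is not before last dose + 30 days. It is collected and is not a TEAE. This does not depend on c.

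**Step 6: after the change.** With calls allowed on Days 30 to 33, max(0, 30 - c) = 0 throughout. With an inclusive TEAE cut-off, the 7.3 period and the TEAE window end on the same day.

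**The case against.** **The gap is small and partly covered.** Events may be volunteered spontaneously under 7.3. An SAE thought related must be notified whenever the investigator learns of it, and ongoing events are followed under 7.5. Section 1.1.3 gives a mean half-life of about 9 to 11 hours. Day 27 is 27 x 24 = 648 hours after the last dose, or roughly 59 (648 / 11) to 72 (648 / 9) half-lives. Anti-IL-1 therapy may also have been resumed after the Day 7 visit. All of this stands. It limits how much late events can say about ATI-450, but it does not make the protocol's own clocks agree.

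**Readings that go too far.** A reader might infer three stronger points.

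- *That on-schedule patients drop out of the per-protocol set.* Section 8.2 asks that patients "complete 12-weeks of treatment and 4-weeks of follow up". On a bare day count, a Day 83 visit (83 < 84) or a Day 27 call (27 < 28) falls short. But no section states 84 or 28 days as the PP threshold. Section 3.1 itself says "At the end of 12-weeks, Day 84 (+/- 1 day), patients will stop ATI-450", and Table 1 puts the Day 30 (+/-3) call under its 4-week follow-up heading. In the protocol's own usage, a patient seen within the windows has met both terms. The two terms also turn on two separate windows, and among call days only Day 27 is below 28.
- *That 10% of observation is lost.* The fraction 3 / 30 counts only post-treatment days and ignores the treatment period, in which AEs are also collected. For the TEAE tables the loss is at most 2 days.
- *That events outside the TEAE window go unreported.* The frequency tables use TEAEs, but the 8.4.2 listings of deaths, SAEs and AEs leading to discontinuation are not expressly limited to them.

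**Conclusion.** The inconsistency is real and minor. A call on Days 27 to 29 complies with the schedule yet ends active inquiry before the reporting period in 7.3 closes. At most 3 days are affected, about 2.6% of some 114 collection days, and at most 2 of those are TEAE days. A Day 30 onset is collected but not treatment-emergent.

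The figures assume a completer with 84 days of treatment and a call that covers its own calendar day. For someone who stops early, the same 3 days would be a larger share of a shorter total. How often calls would fall on Days 27 to 29 cannot be told from the documents, so these are upper limits per patient and not expected losses.

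The primary endpoint row in Section 2 states no time window, so the mismatch lies between the call timing, 7.3 and 8.4.2. The documents do not support extending the point to the PP population.

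**What to change.** 1. Set the Visit 8 call window to Day 30 (+3 days) in Table 1, the synopsis and Section 3.1.
2. In the synopsis and Section 8.4.2, define TEAEs as onset from the first dose through last dose + 30 days inclusive, to match 7.3.

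The cost is wording in four places. The earliest call moves from Day 27 to Day 30, so a call may be up to 3 days later and sites have 4 permitted days instead of 7. The latest permitted call is already Day 33, so the maximum time in study does not change.

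The SAP foreseen in 8.1 could settle the TEAE cut-off, but it cannot recover days that nobody asked about. The call window therefore belongs in the protocol.

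Leave the PP rule in 8.2 alone on this account. Requiring Visits 6 and 8 within their windows could exclude a patient seen on Day 86 or called on Day 34, whom the present rule keeps.

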5.2.2 Patient Completed Efficacy Questionnaires

When these assessments are required at the times outlined in Table 1, they should be the first tasks done at any visit, and prior to study medication dosing.

The KSS is derived from the patient-administered DHAF (Appendix 2), and is the average on a 0 to 10 scale (0 = None, 10 = Very Severe) of 5 separate scales – rash, feeling of fever and chills, joint pain, eye redness and pain, and fatigue.

The DHAF is designed using a linear rating scale of circles in half-step units (e.g. 0.5, 1.0, 1.5, 2.0, etc.), which are marked 0 (none, no severity) to 10 (very severe)^{2.5}. Patients will select the circle on the scale that they determine most accurately represents severity of the symptom that they have experienced during the last 24 hours.

The DHAF will be completed daily by the patient. Daily KSS will be calculated by averaging the sum of the 5 individual symptom scores. KSS during a specified time period will further be calculated by averaging the sum of daily KSS scores during the time period.

Patients will be provided a quiet, private place to complete the assessments. Patients will be instructed to answer all the questions to the best of their ability and without help from others (study staff, family, or friends). The study staff should review the questionnaires after they are completed and encourage patients to complete any missing information. Patients can refrain from answering any question. Study staff will record the refusal of patients to answer any question in the source documents.

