5.2.2.1 Re-emergence of CAPS Symptoms

Re-emergence of CAPS symptoms will be assessed after ATI-450 is discontinued following completion of the treatment period. Re-emergence is defined as an increase in daily KSS of ≥ 3 from baseline for at least two consecutive days.

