6.6 Concomitant Medication

The following medications are prohibited during the duration of the study:

- 1. Systemic immunosuppressant or immunomodulatory therapy (excluding anti-IL-1 therapy for treatment of CAPS during screening and follow-up period). See section 3.1 for washout information.
- 2. JAK inhibitors (systemic and topical).
- 3. Systemic corticosteroids (Intranasal, inhaled, and topical ocular corticosteroids) are allowed.

All medication (including vaccines, over-the-counter or prescription medicines, vitamins, and/or herbal supplements) taken from 30 days before start of screening until the end of the follow-up period will be recorded in the appropriate section of the eCRF. The following details must be recorded in the eCRF:

- Medication name (ideally the generic name)
- Reason for use
- Start and end date of administration
- The dose and frequency of administration

The medical monitor should be contacted if there are any questions regarding prior or concomitant medication or procedures.

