8.4 Statistical Methods

8.4.1 Efficacy Analyses

All efficacy summaries will be conducted on both the ITT and PP populations.

- Proportion of participants in disease remission over time; where disease remission is defined as having a PGA score of minimal or better and a hsCRP and SAA value within the normal range or within 30 percent of the baseline value (ITT and PP population).
- Proportion of participants in clinical remission over time; where clinical remission is defined as having a PGA score of minimal or better (ITT and PP population).
- Time to relapse; where relapse is defined as a two-point worsening on the PGA scale in the ITT population.

- Proportion of participants who experience a daily increase in KSS \geq 3 on at least two consecutive days after discontinuation of ATI-450 over time (PP population).
- Proportion of participants who maintain a mean KSS of no more than 2 higher than baseline for at least 6 out of 8 weeks in the ITT and PP population.
- Change from baseline in PGA and KSS scores will be reported descriptively over time (ITT and PP population).
- Change from baseline in hsCRP and SAA and percent change from baseline in hsCRP and SAA will be summarized over time using continuous statistical summary measures. Determination of sustained treatment effect for hsCRP and SAA will be based upon the median percent change from baseline in the ITT and PP population.

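### Re-emergence after stopping ATI-450 has no rule for an early anti-IL-1 restart, so diary scores under restarted therapy can count as no re-emergence

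*Combined protocol and SAP*

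**What the plan says.** - **Definition.** Protocol section 5.2.2.1 requires a rise in daily KSS of 3 or more "from baseline for at least two consecutive days", assessed once ATI-450 has stopped. No other route to an event is given.
- **Analysis.** Section 8.4.1 counts patients with that rise "on at least two consecutive days after discontinuation of ATI-450 over time (PP population"). The same section opens with "All efficacy summaries will be conducted on both the ITT and PP populations".
- **Restart.** Section 3.1 asks patients to hold off anti-IL-1 therapy until the Day 7 follow-up assessments are done. With a safety concern, and at the investigator's discretion, they may return "early or restart their anti-IL-1 therapy prior to completing the safety follow-up Day 7 visit". The term safety concern is not defined.
- **Prohibited medication.** Section 6.6 bars systemic immunomodulators but makes an exception, "excluding anti-IL-1 therapy for treatment of CAPS during screening and follow-up period".
- **Diary.** Section 3.1 states: "Patients will continue to complete their diary until completion of the safety follow up Day 7 visit".
- **PP set and missing data.** Section 8.2 asks for 12 weeks of treatment, 4 weeks of follow-up and completed assessments, and does not mention a restart. Section 8.4.5 allows no imputation in PP and multiple imputation, where appropriate, in ITT.

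**The concern.** The endpoint asks whether symptoms return once ATI-450 is withdrawn. A patient whose symptoms return quickly may be put back on anti-IL-1 therapy before a second qualifying diary day. If the score then falls, the written rule reads the lower scores as absence of re-emergence, although they describe the patient under restarted therapy. A flare that prompted rescue would then be reported as no flare.

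The study has one arm and at most 10 patients, and this is the endpoint aimed at the period after withdrawal. One misclassified patient therefore moves the proportion visibly. No formal test depends on it: the endpoint is secondary in Table 2 and exploratory in the synopsis, and it is summarised descriptively.

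**Working it through.** The plan gives no figure to reproduce, because the sample size rests on feasibility (section 8.3). The check follows the rules for one patient and then sizes the effect.

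**Step 1: follow one patient.** The KSS is at least 3 above baseline on one follow-up day. The investigator judges this a safety concern and restarts anti-IL-1 therapy.
- The restart does not breach the prohibited-medication rule, given the exception in section 6.6.
- The diary continues to the Day 7 visit. If the KSS falls, there is only one qualifying day and the definition is not met.
- If the patient stays in PP, the result is a non-event.
- Other outcomes are possible but less certain: exclusion from PP for incomplete assessments, a missing result left unimputed in PP, or imputation in an ITT summary. None counts the rescue as an event. Imputation would not alter scores actually observed after the restart.

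**Step 2: who can be affected.** The diary asks about the "severity of the symptom that they have experienced during the last 24 hours", and at visits the patient questionnaires come early: "they should be the first tasks done at any visit, and prior to study medication dosing". A patient who returns on the day after the first qualifying day would normally record the second entry before any restart. An entry made the day after a restart can also still reflect symptoms from before it and complete the pair. So only a restart on or about the first qualifying day, or earlier, matters. An early return alone loses the second entry only if it falls on or before the first qualifying day and is treated as the Day 7 visit that ends the diary.

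With one entry a day, 7 entries give 6 consecutive pairs. The +4-day visit window could give up to 11 entries and 10 pairs. A restart after the entry on follow-up day d leaves d − 1 untreated pairs. For d = 3 that is 2 of 6, or 2 of 10.

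**Step 3: size.** Let N be the number analysed and e the number who would meet the rule without rescue. Scoring one of them as a non-event changes e/N to (e − 1)/N, a fall of 1/N:
- N = 10: 1/10 = 10 points
- N = 8 (assumed PP size): 1/8 = 12.5 points

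If the patient is dropped from PP instead, the fall is e/N − (e − 1)/(N − 1) = (N − e)/(N(N − 1)). At N = 10 this is 10.0 points for e = 1, 5/90 = 5.6 points for e = 5, and 0 for e = 10.

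Illustration with assumed counts, N = 10, e = 6, two of the six restarting early (Clopper-Pearson 95% intervals):

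| Handling of the two | Proportion | 95% interval |
|---|---|---|
| Counted as events | 6/10 = 60% | 26% to 88% |
| Counted as non-events | 4/10 = 40% | 12% to 74% |
| Dropped from PP | 4/8 = 50% | 16% to 84% |

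**Step 4: what a second summary would show.** With x patients meeting the KSS rule and r further patients restarting for CAPS symptoms, the KSS rule gives x/N and counting the restarts gives (x + r)/N. At N = 10 and x = 4:
- r = 0: 40% and 40%
- r = 1: 40% and 50%
- r = 2: 40% and 60%

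This is not a full bracket. If one more patient restarts for another reason, that patient's untreated follow-up is also cut short. With x = 4 and r = 1, the proportion without rescue could then be as high as (4 + 1 + 1)/10 = 60%, above the 50% shown.

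**The case against.** The affected case needs several things to coincide. A CAPS flare must be taken as a safety concern, which the text never says. Section 3.2 does treat relapse as harmful, but it speaks of long-term consequences of prolonged relapse, which hardly compels rescue on the first bad day. The restart must come very early, the next entry must fall below the threshold, and the patient must otherwise have gone on to qualify. PP membership after a restart is not settled by section 6.6, because that exception covers the whole follow-up period, in which resuming therapy after the Day 7 visit is planned. The separate SAP announced in section 8.1 is not in the supplied text and may hold a rule. Restart dates and reasons for use are already recorded, and with at most 10 patients each case can be looked at individually.

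Most of this stands and limits the point to a narrow gap. It does not close it: nothing supplied says how a restart is scored, and the definition applied as written gives a non-event. Section 1.2 describes anti-IL-1 therapy as acting rapidly, so a prompt fall in KSS is credible.

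A reader might infer that a restart should itself become part of the main definition. The documents do not support that. The endpoint is patient-reported symptom return on a stated threshold, and an open-label treatment decision could count a patient with only a small KSS rise.

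**Conclusion.** The gap is real but minor. As written, a patient who restarts anti-IL-1 therapy before a second qualifying day, improves, and is kept in PP counts as no re-emergence on scores obtained under restarted therapy. For each such patient who would otherwise have qualified, the proportion is too low by 1/N: 10 points at N = 10, or 12.5 points at an assumed N = 8.

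This rests on three assumptions: a CAPS flare can be handled as a safety concern, the patient stays in PP, and the unseen SAP adds no rule.

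A reader might infer that the reported proportion is known to be biased downwards. The documents do not show that: the number affected may be zero, and a rescued patient might never have met the rule. Nor do the two summaries proposed below bracket all the uncertainty. They show only how sensitive the result is to CAPS-related restarts.

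**What to change.** In sections 5.2.2.1 and 8.4.1, and in the SAP:

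1. Keep the two-consecutive-day KSS rule as the main definition, but do not use diary days after an anti-IL-1 restart as evidence of no re-emergence.
2. Add a supplementary summary that counts a restart documented as due to returning CAPS symptoms as re-emergence on the restart date, with these patients kept in the denominator.
3. List every early restart with its date, its reason and the KSS up to the restart. Flag patients who restarted for other reasons as having truncated follow-up, and do not treat them as full non-events.
4. Add one eCRF item for why the restart was early. Section 6.6 already captures start date and reason for use, but an entry of CAPS would not explain the timing.

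The cost is wording, one eCRF item and a little more analysis, with no added visits or patients. The downside is some open-label investigator discretion, confined to the supplementary summary.
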